6.3.6 Ophthalmologic examination

Full ophthalmic assessment, including slit lamp examination, should be performed at screening and if a patient experiences any visual symptoms (including blurring of vision), with additional tests if clinically indicated. Any clinically significant findings, including those confirmed by the ophthalmologist must be reported as an AE. Photographs should be performed to record any clinically significant findings. These photographs should be available for central review by AZ and AZ representatives if necessary. Ophthalmology examination results should be collected in the eCRF.

6.3.7 Echocardiogram/MUGA Scan

For extension cohort patients, an Echocardiogram or MUGA scan to assess LVEF will be conducted at baseline (prior to first dose of AZD9291), 12 weeks after the first dose of AZD9291 and 12-weekly thereafter (\pm 1 week). The modality of the cardiac function assessments must be consistent within a patient i.e. if echocardiogram is used for the screening assessment then echocardiogram should also be used for subsequent scans if required. The patients should also be examined using the same machine and operator whenever possible.

6.3.8 Follow-up

6.3.8.1 Safety Follow-Up

A post study assessment will be performed at the time investigational product is permanently discontinued (Study Plan Table 2, Table 3 and Table 4).

In addition for safety follow-up as a minimum, telephone contact should be made with the patient 28 +/-7 days following the discontinuation of AZD9291 to follow up on any SAE/AE's and concomitant medications (including any subsequent cancer therapy). Any SAEs will be followed to resolution where possible.

6.3.8.2 Progression follow-up

Patients who discontinue AZD9291 for reasons other than progression will continue RECIST 1.1 assessments every 6 weeks (relative to first dose of multiple dosing). Details of concomitant medications (including any subsequent cancer therapy) should continue to be collected as detailed in the study plan (see Table 2, Table 3 and Table 4) up to the 28-day follow up visit. Only new SAEs due to study procedures should be collected. For those patients in the expansion cohorts an additional PRO QoL questionnaire should be completed on progression (Table 3). Beyond the 28-day follow up visit only subsequent cancer therapy should be collected.

6.3.8.3 Survival follow-up

In the Phase II extension, following disease progression, the patient, patient's family, or the patient's current physician must be contacted every 6 weeks for survival information, for collection of details of subsequent treatment regimens received following withdrawal from

study drug and to follow up unresolved AEs (unless the patient withdraws consent) regardless of date of last contact, as detailed in the study plan (see Table 4).

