5.1.6.1 Escalation and expansion patients

[figure not shown]
If any other toxicity resolves or reverts to \leq CTCAE grade 2 within 21 days of onset and the patient is showing clinical benefit, treatment with AZD9291 may be restarted at the same dose or a lower dose using the rules below for dose modifications (see Figure 2) and agreement with the AstraZeneca Study Team Physician as needed.

[figure not shown]
If any other toxicity does not resolve to \leq CTCAE grade 2 after 21 days, then the patient should be withdrawn from the study and observed until resolution of the toxicity

On resolution of toxicity within 21 days:

- If a further episode of the same AE subsequently requires dose interruption, AZD9291 must restart at one dose level lower (unless in Cohort 1, when restart will be at Cohort 1 dose) on improvement of the AE.
- If a different AE subsequently requires dose interruption, AZD9291 may restart at the same or one dose level lower (unless in Cohort 1, when restart will be at Cohort 1 dose) on improvement of the AE at the discretion of the Investigator.

Patients who are at the lowest possible dose ie, who have their dose previously reduced to the Cohort 1 dose and who have demonstrated an acceptable response to the dose interruption may be permitted to restart at the lowest dose level at the discretion of the Investigator.

5.1.6.2 Phase II extension patients:

If any other toxicity resolves or reverts to \leq CTCAE grade 2 within 21 days of onset, treatment with AZD9291 may be restarted at the same dose (80 mg) or a lower dose (40 mg) following discussion and agreement with the AstraZeneca Study Team Physician as needed. There will be no individual modifications to dosing schedule in response to toxicity, only potential dose

reduction or dose interruption. If the toxicity does not resolve to \leq CTCAE grade 2 after 3 weeks, then the patient should be withdrawn from the study and observed until resolution of the toxicity.

On resolution of toxicity within 3 weeks:

• If an AE subsequently requires dose interruption, AZD9291 may restart at the same dose or the reduced dose, on resolution/improvement of the AE at the discretion of the Investigator.

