5.1.7 Duration of therapy

Patients should continue on treatment with AZD9291 until RECIST 1.1 defined progression or until treatment discontinuation criteria is met. There is no maximum duration of treatment as patients may continue to receive AZD9291 beyond RECIST 1.1 defined progression as long as they are continuing to show clinical benefit, as judged by the investigator.

If AZD9291 is discontinued for reasons other than disease progression, the patient must continue RECIST 1.1 assessments every 6 weeks until disease progression, even if further lines of anticancer therapy are administered.

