5.4.1 Procedures for discontinuation of a patient from investigational product

Once study medication is permanently discontinued it cannot be restarted.

A patient who discontinues study treatment is not always automatically withdrawn from the study. If a patient is withdrawn from study, see Section 5.4.3

Any patients who discontinue study treatment for reasons other than objective disease progression should have tumour assessments scans performed as scheduled in the protocol (see Table 2, Table 3 and Table 4 until objective disease progression is documented or death occurs, unless consent is withdrawn. Study procedure related SAEs and concomitant medication must be captured until the patient no longer has RECIST 1.1 assessments (disease progression or permanent withdrawal from the study).

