	Screening		ole Dose/(21 day cyc	-	Cycles 2-6 (21 day cycle)	Cycle 7 and every 6 weeks onwards	Discontin uation	28-day Follow up	Progress ion	Post progression survival F/U	Detail in section
Day	-28 to -1	D1	D8	D15	D1	D1				6 weekly relative to progression	
Tumour biopsy (optional)	X			Х			Х				6.8.1. 1
Vital signs	Х	X	Х	X	Х	Х	Х				6.3.3
Height	Х										6.3.3
Weight	X	Х			Х	Х	Х				6.3.3
Clinical chemistry /Haematology/Urinalysis	X	Х	X	Х	Х	Х	Х				6.3.5
ECG	Х	Х	Х	Х	Х	Х	Х				6.3.4
Echocadiogram/MUGA	Х	-	12 v	veekly rel	ative to first d	lose					6.3.7
PK blood sample (including metabolites)		Х	Х	Х	X (cycle 2 only)						6.6.1
Blood sample for cfDNA	Х	Х			6 wkly at RECIST visit X						6.8.1. 2
Genetic consent and blood sample (optional)	X										6.8.2
CSF (optional)		X (once only)								6.8.3	
RECIST assessments	Х	Every 6 weeks (relative to first dose) until progression)									6.10.1

Table 4Study Plan Phase II Extension Cohort

	Screening		ple Dose/C 21 day cyc	-	Cycles 2-6 (21 day cycle)	Cycle 7 and every 6 weeks onwards	Discontin uation	28-day Follow up	Progress ion	Post progression survival F/U	Detail in section
Day	-28 to -1	D1	D8	D15	D1	D1				6 weekly relative to progression	
Cognitive patient interview (optional)					4-0	6wks + 4-6 month	15				6.5.3
Dispense study medication		Х			Х	Х					5
Dose with AZD9291		-			Daily	v dosing					5
Concomitant medication	•										4.3.1
Adverse events											6.4
Survival										Х	6.3.8. 3

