7.7.2 Progression Free Survival

PFS is defined as the time from date of first dosing until the date of objective disease progression as defined by RECIST 1.1 or death (by any cause in the absence of progression) regardless of whether the subject withdraws from AZD9291 therapy or receives another anti-cancer therapy prior to progression.

Patients who have not progressed or died at the time of analysis will be censored at the time of the latest date of assessment from their last evaluable RECIST assessment. If the patient has no evaluable visits or does not have baseline data they will be censored at 0 days unless they die within two visits of baseline.

If a patient discontinues treatment prior to progression and/or receives a subsequent therapy prior to progression then these patients will continue to be followed until evidence of objective disease progression as defined by RECIST 1.1 and their PFS time will be derived as defined above.

Note: Symptomatic deterioration will not be regarded as a progression event.

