7.7.5 Overall Survival

Overall survival will be assessed based on the date of first dose and survival status at the time of analysis.

Overall survival is defined as the interval between the date of first dose and the date of patient death due to any cause. Patients who have not died at the time of the statistical analysis will be censored at the time they were last known to be alive.

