4. TUMOUR RESPONSE EVALUATION

4.1 Schedule of evaluation

CT examinations of the chest and abdomen (including liver adrenal glands) will be used to assess tumour burden at baseline and follow-up visits. CT examination with intravenous contract media administration is the preferred method. MRI should be used where CT is no feasible or it is medically contra-indicated.

Clinical Study Protocol Appendix F Drug Substance AZD9291 Study Code D5160C00001 Edition Number 1 Date

Baseline tumour assessments should encompass all areas of known predilection for metastases in the disease under evaluation and should additionally investigate areas that may be involved based on signs and symptoms of individual patients and should be performed no more than 28 days before the start of study treatment. Follow-up assessments should be performed every 6 weeks (\pm 7 days) after the start of treatment until discontinuation of study treatment or withdrawal of consent. Any other sites at which new disease is suspected should also be adequately imaged at follow-up.

If an unscheduled assessment was performed and the patient has not progressed, every attempt should be made to perform the subsequent assessments as their scheduled visits. This schedule is to be followed in order to minimise any unintentional bias caused by some patients being assessed at different frequency than other patients.

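### In the Phase II extension, survival contacts start only at progression, so a patient who stops attending scans without documented progression has no scheduled vital-status check after the 28-day call

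*Protocol*

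**What the plan says.** **Survival contact.** Section 6.3.8.3 requires that, in the extension, "following disease progression, the patient, patient's family, or the patient's current physician must be contacted every 6 weeks for survival information". The last column of Table 4 (section 6.1) sets the timing as "6 weekly relative to progression". No other survival contact is scheduled.

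**Patients off drug without progression.** Section 5.1.7 says "the patient must continue RECIST 1.1 assessments every 6 weeks until disease progression, even if further lines of anticancer therapy are administered". Section 5.4.1 has scans continue "until objective disease progression is documented or death occurs, unless consent is withdrawn". Sections 6.3.8.2 and 6.10.1 agree, and Appendix F section 4.5 keeps patients with symptomatic deterioration in RECIST follow-up. Beyond the 28-day visit, section 6.3.8.2 limits collection to subsequent cancer therapy, apart from the scans themselves.

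**Text that points the other way.** Appendix F section 4.1 runs the scans only "until discontinuation of study treatment or withdrawal of consent". Section 5.1.6.2 says that if toxicity has not resolved after 3 weeks, "then the patient should be withdrawn from the study and observed until resolution of the toxicity" (the same words stand in 5.1.6.1). Section 5.4.3 describes withdrawal from the study as covering both product and assessments.

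**Deaths and censoring.** Section 6.4.3 records deaths during the study or within 28 ± 7 days after stopping drug. For OS, section 7.7.5 says that patients who have not died "will be censored at the time they were last known to be alive". PFS (7.7.2) and duration of response (7.7.3) count death without progression as an event, and 7.7.2 adds that "Symptomatic deterioration will not be regarded as a progression event".

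**The concern.** Survival contact normally exists to catch patients who no longer come to clinic. Here it opens only after an event that is itself established by attending clinic for a scan. A patient who is too ill to be scanned, declines scans, transfers care, or is withdrawn from the study for unresolved toxicity may never have a progression date, and so never reaches the survival schedule. Once the 28-day window has passed, no scheduled contact would bring a death to light, and the patient is censored at the last date known alive.

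OS is a secondary endpoint collected only in this cohort, as a single-arm Kaplan-Meier summary. If the patients lost in this way are the ones declining, the censoring is informative, and there is no control arm in which the same error could offset.

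**Working it through.** The protocol states no OS target, event count or rate of leaving follow-up, so there is no figure of its own to reproduce. The check is first textual, then an illustration of size.

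**Where the schedule leaves a gap (extension)**

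| Situation | Planned source of vital status |
|---|---|
| On drug | Clinic visits |
| Off drug, no progression, attending scans | 6-weekly RECIST visits (5.1.7, 5.4.1, 6.3.8.2) |
| Progressed | 6-weekly survival contact (6.3.8.3) |
| Off drug, no progression, not attending scans | Telephone contact at 28 ± 7 days (6.3.8.1), then none |

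The last row is the gap. A site that follows Appendix F 4.1 would put into it every patient who stops drug before progression.

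**Size, under assumptions**

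Inputs from the protocol: background median OS of about 16 months (second line) or 10 months (third line), section 5.3.3; about 175 patients, section 7.2.4; the 28-day call, 6.3.8.1.

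Assumptions: a nominal fraction f (5% or 10%) leaves at a time U, uniform over months 1 to 9; leavers carry the base risk until they leave; median time to death after leaving is 3 months; leaving coincides with stopping drug, so OS is censored at the call, c = 28/30.44 = 0.92 months later.

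Hazards: λ = ln 2/16 = 0.0433 and h = ln 2/3 = 0.2310 per month.

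1. Actual leavers. Some die first, so the actual fraction is f × E[exp(−λU)] = f × (0.9576 − 0.6771)/(8 × 0.0433) = 0.81f. That is 4.0% or 8.1%, or about 7 or 14 of 175.

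2. True 12-month OS: (1 − f)·exp(−12λ) + f·E[exp(−λU − h(12 − U))].
 - exp(−12λ) = 2^(−0.75) = 0.5946.
 - The expectation is 0.0625 × (5.417 − 1.207)/(8 × 0.1877) = 0.175.
 - f = 5%: 0.95 × 0.5946 + 0.05 × 0.175 = 57.4%.
 - f = 10%: 0.90 × 0.5946 + 0.10 × 0.175 = 55.3%.

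3. What Kaplan-Meier estimates. At time t the risk set holds base-risk patients, B(t) = [(1 − f) + f·P(U > t)]·exp(−λt), and leavers not yet censored, L(t) = f·E[exp(−λU − h(t − U)); t − c ≤ U ≤ t]. The curve tends to exp(−∫(λB + hL)/(B + L)). Numerical integration gives:

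| Background median | f nominal | Median OS, observed vs true (months) | 12-month OS, observed vs true |
|---|---|---|---|
| 16 | 5% | 15.8 vs 15.0 | 59.0% vs 57.4% |
| 16 | 10% | 15.6 vs 14.1 | 58.5% vs 55.3% |
| 10 | 5% | shift about 0.3 | – |
| 10 | 10% | shift about 0.5 | – |

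4. Checks. Without the 28-day call, the observed curve returns the base 16.0 months and 59.5%, as it should. The call captures 1 − 2^(−0.92/3) = 19% of leavers' deaths. If median time to death after leaving is 6 months (h = ln 2/6), the 10% case with a 16-month background still shifts the median by about 1.0 month.

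5. Direction. In a second model, a patient leaves before progression with probability 2% to 15%, and the death hazard is multiplied by k after leaving. At 15% leaving and a 16-month median, the bias in median OS is −0.6 months at k = 0.5, 0 at k = 1, +0.7 at k = 2 and +1.3 at k = 4. The sign depends on the prognosis of those who leave.

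**The case against.** The strongest reply is that the design hands patients from scan follow-up to survival follow-up without a break. Scans are mandatory until progression or death, even on new therapy; symptomatic deterioration explicitly stays in RECIST follow-up; and all deaths during the study are to be recorded. Section 5.5 says all patients continue to be followed for an update at 12 to 24 months, section 7.7.5 speaks of survival status at the time of analysis, and section 7.9 plans counts of patients who died, remain in survival follow-up, are lost or withdrew consent.

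Much of this stands. A reader might infer that patients without progression are never followed for death; the documents do not support that, because the gap affects only those who stop attending scans, and only after the 28-day window. Where consent is withdrawn, contact would stop under any plan. A reader might also infer that OS and PFS are certainly biased upward. That requires leavers to do worse, and the protocol has no data on it. For PFS and duration of response, survival calls recover deaths but not undocumented progressions. A death found long after the last scan would count at its own date, since section 7.7.2 has no missed-visit rule outside the baseline case.

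What the reply does not supply is a contact. Sections 5.5, 7.7.5 and 7.9 presuppose vital status at analysis but schedule nothing that would obtain it for a patient who has left scans. Appendix F 4.1 and the withdrawal wording in 5.1.6.2 make such patients more likely.

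**Conclusion.** The point holds as a gap in the trigger for survival contact, not as a demonstrated bias. Deaths after the 28-day window can be missed in extension patients who stop scans without documented progression. If those patients have a worse prognosis, as is plausible after symptomatic deterioration, OS is overstated: by about 0.8 to 1.5 months in the median and 1.6 to 3.2 points at 12 months under the 16-month, 3-month-to-death assumptions with nominal 5% to 10% leaving, and by about 0.3 to 0.5 months in the median with a 10-month background. If leaving is unrelated to prognosis there is no bias; if leavers do better, it runs downward. The leaving rate and survival after leaving are assumptions throughout. ORR is untouched. The change is worth making because it is cheap and vital status missed during follow-up may not be recoverable later.

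**What to change.** - In section 6.3.8.3 and the last column of Table 4, start 6-weekly survival contact at progression or at the end of RECIST follow-up for any reason, whichever comes first. Time it from that date and continue unless consent to survival contact itself is withdrawn. Rename the column to match.
- Require a vital-status check on all dosed extension patients at each OS data cut-off.
- Reconcile Appendix F 4.1 with sections 5.1.7, 5.4.1, 6.3.8.2 and 6.10.1 on how long scans continue, and state what withdrawal from the study in section 5.1.6.2 means for scan and survival follow-up. This concerns data collection only, not the treatment rule.

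The cost is a sentence, a column heading, two clarifications, and a few extra telephone or record contacts for a small number of patients.

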6.4 Adverse events

The Principal Investigator is responsible for ensuring that all staff involved in the study is familiar with the content of this section.

6.4.1 Definition of adverse events

An adverse event is the development of an undesirable medical condition or the deterioration of a pre-existing medical condition following or during exposure to a pharmaceutical product, whether or not considered causally related to the product. An undesirable medical condition can be symptoms (eg, nausea, chest pain), signs (eg, tachycardia, enlarged liver) or the abnormal results of an investigation (eg, laboratory findings, electrocardiogram). In clinical studies, an AE can include an undesirable medical condition occurring at any time, including run-in or washout periods, even if no study treatment has been administered.

For patients in Japan: For cases where it could be suspected that a tissue-derived medicine has been contaminated by a pathogen, information about any of the above conditions (including infection) should be collected.

Any deterioration of the disease under study and associated symptoms or findings should not be regarded as an adverse event as far as the deterioration can be anticipated (see Section 6.4.3).

The term adverse event is used generally to include any AE whether serious or non-serious.

6.4.2 Definitions of serious adverse events

A serious adverse event (SAE) is an AE occurring during any study phase (ie, run-in, treatment, washout, follow-up), that fulfils one or more of the following criteria:

- Results in death
- Is immediately life-threatening
- Requires in-patient hospitalisation or prolongation of existing hospitalisation
- Results in persistent or significant disability/ incapacity or substantial disruption of the ability to conduct normal life functions
- Is or results in a congenital abnormality or birth defect
- Is an important medical event that may jeopardise the patient or may require medical intervention to prevent one of the outcomes listed above.

For further guidance on the definition of a SAE, see Appendix B of this Clinical Study Protocol.

For definition of other significant adverse events (OAE) see Section 7.3.1

6.4.3 Recording of adverse events

Time period for collection of adverse events

AEs will be collected throughout the study, from informed consent until the end of the followup period. The follow-up period is defined as 28 ± 7 days after study treatment is discontinued. SAEs occurring in the follow-up period should be reported to AstraZeneca in the usual manner (see Section 6.4.4).

Following discontinuation of AZD9291, SAEs considered related to study procedures should continue to be collected while patients are followed up for disease progression.

After the final database lock, there may be some patients remaining on study treatment. For these patients who are continuing to receive AZD9291 AZ will collect information (during the treatment period and for 28 +/- 7 days after last dose) on SAEs, deaths (including those due to disease progression), discontinuation due to AEs/SAEs and drug accountability only.

Follow-up of unresolved adverse events

Any AEs that are unresolved at the patient's last visit in the study are followed up by the investigator for as long as medically indicated, but without further recording in the CRF. AstraZeneca retains the right to request additional information for any patient with ongoing AE(s) at the end of the study, if judged necessary.

If an investigator learns of any SAEs, including death, at any time after a patient has completed the study and he/she considers there is a reasonable possibility that the event is related to AZD9291, the investigator should notify AstraZeneca.

Variables

The following variables will be collected for each AE:

- AE diagnosis/description
- The date when the AE started and stopped
- Maximum CTCAE grade
- Whether the AE is serious or not
- Investigator causality rating against the investigational product (yes or no)
- Action taken with regard to investigational product

• Outcome

For SAEs other variables will be collected including treatment given for the event.

It is important to distinguish between serious and severe AEs. Severity is a measure of intensity whereas seriousness is defined by the criteria in Section 6.4.2. An AE of severe intensity need not necessarily be considered serious. For example, nausea that persists for several hours may be considered severe nausea, but not a SAE. On the other hand, a stroke that results in only a limited degree of disability may be considered a mild stroke but would be a SAE.

The grading scales found in the current National Cancer Institute CTCAE version 4 will be utilised for all events with an assigned CTCAE grading. For those events without assigned CTCAE grades, the recommendation in the CTCAE criteria that converts mild, moderate and severe events into CTCAE grades should be used. A copy of the current CTCAE version can be downloaded from the Cancer Therapy Evaluation Program website (http://ctep.cancer.gov).

Causality collection

The investigator will assess causal relationship between investigational product and each adverse event, and answer 'yes' or 'no' to the question: 'Do you consider that there is a reasonable possibility that the event may have been caused by the investigational product?'

For SAEs causal relationship will also be assessed for other medication and study procedure. Note that for SAEs that could be associated with any study procedure the causal relationship is implied as 'yes'.

A guide to the interpretation of the causality question is found in Appendix B of this Clinical Study Protocol.

Adverse events based on signs and symptoms

All AEs spontaneously reported by the patient or care provider or reported in response to the open question from the study personnel: 'Have you had any health problems since the previous visit/you were last asked?', or revealed by observation will be collected and recorded in the CRF. When collecting AEs, the recording of diagnoses is preferred (when possible) to recording a list of signs and symptoms. However, if a diagnosis is known and there are other signs or symptoms that are not generally part of the diagnosis, the diagnosis and each sign or symptom will be recorded separately.

Adverse events based on examinations and tests

The results from protocol mandated laboratory tests, vital signs, ECGs and other safety assessments will be summarised in the Clinical Study Report. Deterioration as compared to baseline in these parameters will therefore only be reported as AEs if they fulfil any of the criteria for a SAE, a DLT or are the reason for discontinuation of treatment with the investigational product unless clearly due to progression of disease under study (see Disease progression).

If deterioration in a laboratory value, vital sign, ECG or other safety assessment is associated with clinical signs and symptoms, the sign or symptom will be reported as an AE and the associated laboratory result or other finding will be considered as additional information. Wherever possible the reporting investigator uses the clinical, rather than the laboratory term (eg, anaemia versus low haemoglobin value). In the absence of clinical signs and symptoms, clinically relevant deteriorations in non-mandated parameters should be reported as AE(s).

Deterioration of a laboratory value that is unequivocally due to disease progression should not be reported as an AE.

Any new or aggravated clinically relevant abnormal medical finding at a physical examination as compared with the baseline assessment will be reported as an AE.

Disease progression

Disease progression can be considered as a worsening of a patient's condition attributable to the disease for which the investigational product is being studied. It may be an increase in the severity of the disease under study and/or increases in the symptoms of the disease. The development of new, or progression of existing metastasis to the primary cancer under study should be considered as disease progression and not an AE. Events that are unequivocally due to disease progression should not be reported as AEs during the study.

New cancers

The development of a new cancer should be regarded as an AE and will generally meet at least one of the serious criteria. New cancers are those that are not the primary reason for the administration of the study treatment and have been identified after the patient's inclusion in this study. They do not include metastases of the original cancer.

Handling of deaths

All deaths that occur during the study, or within the follow-up period after the administration of the last dose of investigational product, should be reported as follows:

- Death, which is unequivocally due to disease progression, should be communicated to the study monitor at the next monitoring visit and should be documented in the CRF module, but should not be reported as a SAE during the study
- Where death is not clearly due to disease progression of the disease under study the AE causing the death should be reported to the study monitor as an SAE within 24 hours. The report should contain a comment regarding the co-involvement of progression of disease, if appropriate, and should assign a single primary cause of death together with any contributory causes
- Deaths with an unknown cause should always be reported as a SAE but every effort should be made to establish a cause of death. A post-mortem may be helpful in the assessment of the cause of death, and if performed a copy of the post-mortem

results (with translation of important parts into English) should be reported in an expedited fashion to an AstraZeneca representative within the usual timeframes

